6.9. Ocular Symptom Assessments

Results of the ocular assessments will be presented in data listings.

6.10. Corticosteroid and Lubricating Eye Drop Compliance

All compliance information collected on the CRF will be presented in data listings.

6.11. Transfusions

All transfusions recorded on the CRF will be presented in data listings.

6.12. Physical Examination

Physical examination results will be presented in data listings.

6.13. ECOG PS

ECOG PS results will be presented in data listings. Baseline ECOG PS will be summarized in disease characteristics table (Section 4.1.4).

7. IMMUNOGENICITY

Patients will be grouped into five categories based on ADA status before and post the first dose of MIRV:

- Treatment-emergent ADAs: Patients who had a baseline-negative ADA result who developed ADAs at any time after initial administration of drug.
- Treatment-enhanced ADAs: Patients who had a baseline positive ADA result in whom the assay signal was enhanced (greater than baseline titer by \geq 4 folds) at any time after initial drug administration.
- Treatment-unaffected ADA: Patients who had a baseline-positive ADA result in whom the assay signal was not enhanced (negative or not greater than baseline titer by ≥ 4 folds) at any time after initial drug administration.
- Seronegative: a patient who tests negative at all visits.

If a titer is below LLQ, it will be imputed as half of LLQ.

Efficacy endpoints ORR and DOR will be analyzed by the above ADA status group.

TEAE by SOC and PT will be summarized for the above ADA status group.

8. **BIOMARKERS**

The exploratory biomarker analyses for this study will be covered by a separate, independent analysis plan.

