- ^m If a patient discontinues before documentation of PD, a tumor assessment and CA-125 will be assessed at the EOT or 30-Day Follow-up visit, if not performed within the previous 6 weeks. Tumor assessments and CA-125 will continue to be performed every 12 (\pm 3) weeks until PD is documented per RECIST 1.1 or the patient starts new anticancer therapy. Patients who discontinue MIRV for reasons other than progressive disease (PD) will continue with tumor assessments until documentation of PD or the start of a new anticancer therapy, whichever comes first. Prior to Week 36 (from Cycle 1, Day 1), assessments should occur every 6 weeks (\pm 1 week) as allowed by local requirements but must occur at an interval of no more than 12 weeks. After Week 36, assessment will occur every 12 weeks (\pm 3 weeks) until documentation of PD, death, the start of new anticancer therapy, or patient's withdrawal of consent (whichever occurs first).

- ⁿ CA-125 will be measured at the time of every tumor assessment (± 4 days) (responses will be confirmed according to GCIG criteria [Appendix C](#)).
- ^o Only AEs/SAEs which are considered related to a study procedure (ie blood draw or fresh tumor biopsy) will be captured during the Pre-screening period, ie from the time of signing the Pre-screening consent (if one is utilized) until the signing of the main study informed consent, or until the patient is determined to be a screen failure.
- ^p Blood samples for PK analysis will be taken within 1 hour after MIRV infusion on Day 1 of Cycles 1 and 3, and on Day 8 (± 24 hours) of Cycles 1 and 3. Samples will also be collected prior to dosing on Day 1 of Cycles 2 and 4, and EOT and also at the 30-Day Follow-up, if feasible.
- ^q Immunogenicity will be assessed in PK samples collected prior to dosing (predose) on C1D1, C2D1, C4D1, at EOT, and 30-Day Follow-up.
- ^r Survival follow-up assessments will occur every 3 months (± 1 month) until death, the patient is lost to follow-up or withdrawal of consent for survival follow-up, or EOS (whichever comes first). These assessments may be conducted by telephone. Information on the start of new anticancer therapy (including start date, therapy type/name, and response on treatment) should be collected. Additional survival follow-up calls may occur periodically if needed for regulatory requests or at time of database lock for either primary or final analysis.

TABLE OF CONTENTS

SPONSOR SIGNATURE PAGE	2
SPONSOR CONTACT LIST	3

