6.2. Immunogenicity Assessments – Mirvetuximab Soravtansine

The potential immunogenicity against MIRV will be assessed at C1D1, C2D1, C4D1, EOT, and 30-Day Follow-up, as outlined in [Table 2](#).

An ADA sample should be collected prior to dosing on C1D1. The sample for ADA analysis is taken from the PK tube predose on Day 1 of Cycles 2, and 4 and at the EOT and 30-Day Follow-up visits.

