5.4. Efficacy Analysis on Subgroups of Patients

Efficacy endpoints (ORR, DOR, PFS, OS, and GCIG CA-125 response rate) will be analyzed with the following subgroups of patients:

- Number of prior lines of therapy (1 vs 2 vs 3)
- Prior exposure to PARPi (yes vs no vs uncertain)
 - If patient participated in a double-blind randomized trial comparing PARP inhibitor to placebo and the actual treatment was unknown, patient will be summarized under 'uncertain' category.
- ADA status

The summaries for ORR and GCIG CA-125 response include the response rate and its 95% exact CI.

The summaries for time to event variables (DOR, PFS, and OS) include the number and percentage of events, median and its 95% CI.

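### Efficacy by ADA status uses ADA found at any time after dosing, while late ADA sampling follows the end of treatment, so PFS, OS and ORR can differ between ADA groups with no ADA effect

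*SAP*

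**What the plan says.** **Grouping.** SAP Section 7 opens with "Patients will be grouped into five categories based on ADA status before and post the first dose of MIRV". Four groups follow: treatment-emergent, treatment-enhanced, treatment-unaffected and Seronegative. The treatment-emergent group is "Patients who had a baseline-negative ADA result who developed ADAs at any time after initial administration of drug". The negative group is "Seronegative: a patient who tests negative at all visits", with no minimum number of post-dose samples.

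**Use.** SAP Section 7 adds: "Efficacy endpoints ORR and DOR will be analyzed by the above ADA status group". SAP Section 5.4 goes further: "Efficacy endpoints (ORR, DOR, PFS, OS, and GCIG CA-125 response rate) will be analyzed with the following subgroups of patients", and ADA status is one of the listed subgroups. On content it says: "The summaries for time to event variables (DOR, PFS, and OS) include the number and percentage of events, median and its 95% CI". Neither section sets a landmark, a time-dependent method or a caution on interpretation.

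**Sampling.** Protocol Section 6.2 states: "The potential immunogenicity against MIRV will be assessed at C1D1, C2D1, C4D1, EOT, and 30-Day Follow-up". The immunogenicity row of Protocol Table 2 carries a mark in the column for Cycle 2 onward, but footnote q narrows it: "Immunogenicity will be assessed in PK samples collected prior to dosing (predose) on C1D1, C2D1, C4D1, at EOT, and 30-Day Follow-up". The only other ADA draws follow a Grade 2 or higher infusion-related reaction (Protocol Sections 5.5.5 and 6.1).

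**Status.** SAP Section 3.11.2 plans no formal test on secondary endpoints. SAP Section 3.9 places the ORR analysis about 6 months after the last enrolment. Protocol Section 10.4.2 adds a DOR update 12 months later.

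**The concern.** ADA status here is a post-baseline variable whose later measurements are tied to the outcome. Treatment usually ends at progression, and the end-of-treatment sample is drawn then. Two opposing distortions follow.

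- A patient who stays on drug longer has more time to convert before her end-of-treatment sample. To be found positive late she must first have stayed progression-free and alive. That is immortal time for PFS and OS, and outcome-dependent grouping for ORR and CA-125 response.
- A patient doing well and still on drug at the cutoff has no scheduled ADA result after C4D1. If negative so far, she is Seronegative by definition, whatever her current status.

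A reader could take the resulting tables as evidence that ADA does, or does not, alter efficacy when they partly reflect time on treatment and sample dates. What is at stake is the interpretation of a supportive subgroup table, not the trial's main conclusion.

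**Working it through.** **The plan's own figure.** The documents give no figure for the ADA analysis. The only design calculation is the exact binomial test with 105 patients. Rejecting at 20 or more responders gives one-sided alpha 0.0242 and power 0.906, which agrees with the stated 0.0242 and 91% (protocol) or 90% (SAP). Nothing below touches it.

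**Step 1: the mechanism by hand.** Assume 10% conversion by 6 months at a constant hazard: λ = −ln(1 − 0.10)/6 = 0.01756 per month, and P(converted by t) = 1 − exp(−λt).

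- Non-responder with treatment ending at 2.8 months (assumed median): 1 − exp(−0.0492) = 4.8%.
- Responder at 6 weeks (1.4 months) with DOR 7.8 months, so ending at 9.2 months: 1 − exp(−0.1615) = 14.9%.
- The same responder, if still on drug at the cutoff, can have been found positive only by C4D1 (63/30.44 = 2.07 months): 1 − exp(−0.0363) = 3.6%.

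The first two figures show the immortal time. The third shows the opposing pull.

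**Step 2: simulation with ADA independent of every outcome.** Samples at C2D1, C4D1, end of treatment and 30-day follow-up count only if taken before the cutoff. Infusion-reaction samples and CA-125 response were not modelled. Both models assume 12-month accrual.

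- *Model A.* From Protocol 10.5: ORR 31.4%, median DOR 7.8 months. From Protocol 1.6.2: 12% toxicity discontinuation, applied by 6 months or not at all. Assumed: non-responder median PFS 2.8 months; first response at 6, 12 or 18 weeks (60/30/10%); post-progression survival median 7 months.
- *Model B.* From Protocol 10.1 and 1.6.2: ORR 24%, median DOR 5.7 months, median PFS about 4.8 months. Assumed: ADA 5%, 10% or 30% by 6 months; post-progression survival median 9 months; other discontinuation exponential with mean 30 months.

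First analysis, ADA-positive vs ADA-negative (times in months):

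| Scenario | ORR | Median PFS | Median OS |
|---|---|---|---|
| A, 10%, persistent | 36–38% vs 31% | 6.2–6.3 vs 4.1 | 15.0–15.4 vs 13.6 |
| A, 10%, ADA lasts 12 weeks | 33–35% vs 31% | 5.1–5.2 vs 4.2 | 14.1–14.5 vs 13.7 |
| A, persistent, progression seen only at scans | 33–34% vs 31% | 5.5 vs 4.1 | – |
| A, 12 weeks, progression seen only at scans | 30–31% vs 31% | 5.5 vs 5.5 | – |
| A, onset before C2D1 | 31% vs 31% | 4.2 vs 4.2 | – |
| B, 5% | 30.3% vs 23.8% | 6.7 vs 4.9 | 17.1 vs 15.4 |
| B, 10% | 29.7% vs 23.6% | 6.7 vs 4.8 | 17.4 vs 15.4 |
| B, 30% | 28.7% vs 22.7% | 6.5 vs 4.5 | 17.1 vs 15.0 |

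Re-coding Model A with small changes (conversion stopping at end of treatment, or no toxicity discontinuation) gives PFS 6.6–6.8 vs 4.1 and ORR about 39% vs 31%. In Model B with all conversion complete by C2D1, the groups agree (ORR about 24%, PFS about 5.0 months in both).

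**Step 3: later cutoff** (6 + 12 = 18 months after last enrolment, should the tables be repeated then). Persistent ADA: PFS 9.1 vs 3.9 in Model A; 7.9–8.4 vs 4.1–4.8 in Model B, with ORR 31–32% vs 22–24%.

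**Step 4: DOR.** The direction is unstable:

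- Model A, persistent, first analysis: 6.5–7.1 vs 7.9–8.1 months.
- Model A, persistent, later cutoff: about 10.8 vs 7.3.
- Model A with DOR 5.7, first analysis: about 6.0 vs 5.7 (persistent) or 4.9 vs 5.8 (12 weeks).
- Model B, first analysis: 5.7–6.0 vs 5.7.

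In Model A, 34–44% of responders are still on drug at the first analysis with no scheduled sample since C4D1, so the opposing pull is substantial for this endpoint.

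**Step 5: does a landmark remove it?** Status from samples through C4D1, time counted from C4D1, patients with a C4D1 sample: Model A gives PFS 4.3 vs 4.3 and OS 13.9 vs 13.9; Model B gives PFS 4.5 vs 4.5 and OS 15.0–15.2 vs 15.2. An OS landmark among everyone alive at Week 9 still shows 12.8 vs 12.0, because patients already off drug are no longer sampled in the same way.

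**The case against.** The strongest reply is that this matters little. The tables are descriptive and untested. With 7 positive patients, the ORR gap is 7 × (0.36 to 0.39 − 0.31) = 0.35 to 0.56 of a responder, and 3 responders among 7 has an exact 95% CI of 10 to 82%. Progression is in fact seen only at scheduled scans, which shrinks the ORR gap and, with 12-week ADA, removes both the ORR and the PFS gap. Very early onset leaves nothing. All of that stands, and it is why the point is modest. It does not answer the PFS gap with persistent, accruing ADA, which survives scan timing (5.5 vs 4.1).

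Three stronger readings are tempting, and the documents support none of them.

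- *The undefined fifth category is for incompletely sampled patients, and decides which group has the longer DOR.* No passage describes a fifth category. The count may be a drafting slip, or a bullet may have been lost when the PDF was read. All that can be said is that five are announced and four appear.
- *The SAP has no rule for a patient last sampled at C4D1.* It has one: negative at every visit is Seronegative. The objection is to that rule's bias. The real gaps are patients with no baseline sample and patients with no post-dose sample.
- *DOR is biased in a known direction.* Step 4 shows that it is not.

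**Conclusion.** The concern holds as an improvement worth considering. Followed as written, the plan builds immortal time into PFS and OS by ADA status and outcome-dependent grouping into ORR. CA-125 response is exposed by the same reasoning but was not quantified.

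With no ADA effect and 10% persistent ADA by 6 months at constant onset, median PFS is about 6 to 7 vs 4 months and ORR about 36 to 39% vs 31% at the first analysis, with a larger gap at a later cutoff. The size rests wholly on ADA rate, timing and persistence, none of which the documents give. Transient ADA shrinks both gaps, scan-timed progression shrinks the ORR gap further, and onset before C2D1 essentially abolishes them. The number of positive patients, about 5 to 7, is part of the same assumption. The primary ORR test, its alpha and its power are unaffected.

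**What to change.** 1. Keep the any-time groups for ADA incidence and the TEAE tables, where they are suitable.
2. In SAP Section 5.4, base PFS and OS by ADA status on samples through C4D1, in a landmark analysis starting at C4D1 among patients still at risk who have a C4D1 ADA sample. If one or none of them is ADA-positive, give the patient listing instead of the table.
3. Footnote any ORR, DOR or CA-125 table by any-time ADA status as confounded by time on treatment and sample timing. List ADA-positive patients individually with sample, response and progression dates.
4. As minor clean-up, reconcile the five announced categories with the four listed, state how patients with no baseline or no post-dose ADA sample are classed, and say in SAP Section 5.4 which definition ADA status uses.

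**Cost.** SAP wording, one landmark table and one listing, with no new data. SAP Section 1.1 allows changes before final database lock.

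**Downside.** Late converters count as negative, and early failures leave the landmark set (about 28% of patients are not in it in Model B). Few positives remain: 105 × 0.72 × 0.036 = 2.7 in Model B, and 2.5 to 2.7 in Model A. On a Poisson basis with mean 2.5 to 2.7, the chance of none is about 7 to 8% (e^−2.7 = 0.067, e^−2.5 = 0.082). The chance of at most one is about 25 to 29% (3.7 × 0.067, 3.5 × 0.082). The listing may therefore carry most of the information.

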9. PHARMACOKINETICS

Plasma concentration data collected in this study will be listed and summarized for the PK analysis population. Mean and 95% CI, standard deviation, geometric mean, coefficient of variation (CV, expressed as percentage), median, Q1, Q3, min, and max will be reported by visit. Data points that are below the lower limit of quantitation will be excluded from the analyses.

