The MIRV safety profile was predominantly characterized by low-grade nausea (51%), diarrhea (40%), and blurred vision (40%). These TEAEs are generally managed and mitigated with antiemetics, antidiarrheals, and lubricating/steroid eye drops. In the MIRV group, there were fewer \geq Grade 3 TEAEs, and fewer TEAEs leading to dose reduction or delay and treatment discontinuation (46%, 37%, and 12%, respectively) compared with the IC chemotherapy group (61%, 45%, and 19%, respectively). While myelosuppression is an important safety issue with PLD and Topo, MIRV is associated with less myelosuppression compared to IC chemotherapy, with lower rates of neutropenia (7% vs. 39% all grade; 0% vs. 21% Grade 3+), thrombocytopenia (11% vs. 16% all grade; 0% vs. 4% Grade 3+) and anemia (14% vs. 29% all grade; 2% vs. 11% Grade 3+). Similarly, neurotoxicity is an important safety issue with Pac; MIRV, an ADC with the tubulin-directed payload DM4, is associated with less peripheral neuropathy than Pac (15% vs. 28% Grade 2+) and less alopecia (3% vs. 22% all grades). The safety profile of MIRV in the high FR α subset is consistent with that observed in the overall MIRV safety population.

For MIRV the mean half-life ($t_{1/2}$) was 115.1 hour (4.8 days), with little evidence of accumulation (mean accumulation ratio of 1.102).

There was no apparent relationship between patients testing positive for anti-drug antibodies (ADA) and MIRV exposure.

Please see the [Investigator Brochure](#) for information on Study IMGN853-0403.

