4.1.2. Dose and Schedule for Mirvetuximab Soravtansine

MIRV will be administered at 6 mg/kg on Day 1 of every 3-week cycle (Q3W).

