6. PHARMACOKINETIC, IMMUNOGENICITY, AND BIOMARKER ASSESSMENTS

6.1. Pharmacokinetic Assessments – Mirvetuximab Soravtansine

The PK properties of MIRV and key metabolites will be evaluated following IV administration, as outlined in [Table 2](#) and [Table 8](#). Plasma samples will be collected to determine the concentration of MIRV (conjugate, total Ab, free DM4, S-methyl DM4 and possibly other metabolites).

Blood samples for PK analysis will be taken at the following timepoints:

Table 8: Pharmacokinetics Sampling Time Points

Visit	Time Point
C1D1	Predose (immunogenicity only); ≤ 1 hour after MIRV infusion
C1D8	Anytime during visit
C2D1	Before dosing
C3D1	≤ 1 hour after MIRV infusion
C3D8	Anytime during visit
C4D1	Before dosing
EOT	Anytime during visit
30-Day Follow-up	Anytime during visit

Abbreviations: C = cycle; D = day; EOT = End of Treatment.

Unscheduled visit: Any patient who experiences a ≥ Grade 2 IRR during or within 3 hours after the administration of MIRV will have blood drawn within 3 hours of the onset of the reaction and one week later for determination of drug concentration and ADAs to MIRV.

PK samples may also be obtained as feasible at any time during the treatment period for assessment of treatment-related SAEs if deemed appropriate by the Investigator and Sponsor.

Procedures for collection, storage and shipment of samples are provided in the applicable Laboratory Manual.

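### SAP 9 drops plasma concentrations below the quantitation limit, which biases the affected visit summaries upward and leaves no count of what was removed

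*SAP*

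**What the plan says.** SAP 9 lists and summarizes concentrations for the PK analysis population. At each visit the summary is broad: "Mean and 95% CI, standard deviation, geometric mean, coefficient of variation (CV, expressed as percentage), median, Q1, Q3, min, and max will be reported." The next sentence sets the rule at issue: "Data points that are below the lower limit of quantitation will be excluded from the analyses."

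Protocol 10.2 calculates no PK parameters because sampling is sparse. It promises summary statistics at each nominal time and possibly graphs, and it gives no BLQ rule. Protocol 6.1 sets the analytes: "Plasma samples will be collected to determine the concentration of MIRV (conjugate, total Ab, free DM4, S-methyl DM4 and possibly other metabolites)." Post-infusion and Day 8 samples are taken in Cycles 1 and 3. Table 2, footnote p, adds the later ones: "Samples will also be collected prior to dosing on Day 1 of Cycles 2 and 4, and EOT and also at the 30-Day Follow-up." Four of the eight visits in Protocol Table 8 are therefore predose Cycle 2, predose Cycle 4, End of Treatment and 30-Day Follow-up.

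SAP 3.12.5 admits to the PK population anyone with at least one non-missing concentration, without saying whether a BLQ result counts. For anti-drug antibody titers, SAP 7 has a different rule: "If a titer is below LLQ, it will be imputed as half of LLQ."

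Neither document states an LLOQ or an expected BLQ rate, or plans a BLQ count or a sensitivity summary with BLQ values kept.

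**The concern.** The rule removes values because they are low. Each visit summary then describes only the samples with quantifiable drug, although a reader will take it as describing all sampled patients. The reported minimum can never fall below the LLOQ. If every sample at a visit were BLQ, the row would be empty instead of showing that drug could not be quantified.

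Half of the scheduled visits are troughs or post-treatment samples, where low values are most likely, and the analytes include the free payload and its metabolite. Because no PK parameters are derived, the concentration summaries are the main PK result. Overstated troughs and washout levels with understated relative variability would be carried into any later use of those tables, and nothing in them would show how much was cut.

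**Working it through.** The plan states no figure on this point to reproduce. The check has three parts.

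**1. Direction.** Every excluded value lies below the LLOQ and every retained value lies at or above it. So E[C | C ≥ LLOQ] > E[C] whenever P(C < LLOQ) > 0. The same ordering raises the geometric mean, the median and the quartiles. With no BLQ results nothing changes.

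**2. Where BLQ results are plausible.** Inputs:
- Dosing interval of 21 days (Protocol 4.1.2).
- Mean MIRV half-life, which Protocol 1.6.2 says "was 115.1 hour (4.8 days), with little evidence of accumulation." Check: 115.1/24 = 4.80 days.
- 30-Day Follow-up at 30 to 44 days after the last dose (Protocol 9.3.1).

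Under single-exponential decay the fraction of peak remaining is 2^(−t/4.80):

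| Time since dose | Half-lives | Remaining |
|---|---|---|
| 7 days (Day 8) | 1.5 | 36% |
| 21 days (trough) | 4.4 | 4.8% |
| 30 days | 6.3 | 1.3% |
| 44 days | 9.2 | 0.17% |

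These are rough. The same model predicts accumulation of 1/(1 − 0.048) = 1.05, against the mean ratio of 1.102 in Protocol 1.6.2. They rank the visits; they do not show that any sample is BLQ.

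**3. Size.** Assumptions: log-normal concentrations, BLQ fraction f, and coefficient of variation CV. Let s = √ln(1 + CV²) and z = Φ⁻¹(f). After exclusion:
- arithmetic mean ratio = Φ(s − z)/(1 − f)
- geometric mean ratio = exp[s·φ(z)/(1 − f)]
- median ratio = exp[s·Φ⁻¹(f + (1 − f)/2)]

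Example with CV 50% and f = 10%: s = √ln 1.25 = 0.472, z = −1.282, φ(z) = 0.175. Mean ratio = Φ(1.754)/0.9 = 0.960/0.9 = 1.067. Geometric mean ratio = exp(0.472 × 0.175/0.9) = 1.096.

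| True CV | BLQ | Mean | Geometric mean | Median | SD ratio | CV reported |
|---|---|---|---|---|---|---|
| 50% | 10% | 1.07 | 1.10 | 1.06 | 0.96 | 45% |
| 50% | 20% | 1.13 | 1.18 | 1.13 | 0.94 | 42% |
| 50% | 50% | 1.36 | 1.46 | 1.37 | 0.92 | 34% |
| 100% | 10% | 1.09 | 1.18 | 1.11 | 1.01 | 93% |
| 100% | 20% | 1.19 | 1.34 | 1.24 | 1.03 | 87% |
| 100% | 50% | 1.60 | 1.94 | 1.75 | 1.12 | 71% |

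The CV is understated throughout. The SD falls when the true CV is 50% and rises when it is 100%.

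**Keeping BLQ samples at LLOQ/2 in the same model.** Percentage error, exclusion against LLOQ/2:

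| True CV | BLQ | Mean | Geometric mean |
|---|---|---|---|
| 30% | 10% | +4.7 vs −2.5 | +5.9 vs −5.4 |
| 30% | 50% | +23.1 vs −14.5 | +26.4 vs −20.5 |
| 50% | 10% | +6.7 vs −1.5 | +9.6 vs −4.6 |
| 50% | 50% | +36.3 vs −9.5 | +45.8 vs −14.6 |
| 100% | 10% | +9.2 vs −0.5 | +17.6 vs −2.9 |
| 100% | 50% | +59.5 vs −2.6 | +94.3 vs −1.4 |

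Substitution has the smaller error in every row. It inflates the CV when true variability is low: a true 30% with 20% BLQ is reported as 39%, against 24% under exclusion, so on that statistic exclusion is closer.

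**The case against.** The strongest reply is that the bias may be nil. Without an LLOQ, 5% of peak could be well above the limit, and the half-life is for MIRV; none is given for free DM4 or S-methyl DM4. End of Treatment is timed from the decision to stop (Protocol 9.2), not from the last dose, so low values there are not assured. This stands, and it is why the point is conditional on BLQ results occurring. It does not defend the rule, which only has an effect when they do.

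A second reply is that the summaries are not the sole PK output. That is correct. SAP 9 also lists the data, and Protocol 10.2 allows graphs. The exclusion is worded for the analyses and is not said to reach the listing, so BLQ results may remain visible there. The summary tables still carry no count of them. The default number of non-missing values in SAP 3.13 does not help while it is unclear whether a BLQ result counts as non-missing.

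A third reply is that the titer rule in SAP 7 is no precedent, because it serves a four-fold comparison with baseline on another assay. That is fair. It shows that the authors know the half-limit convention, not that the SAP contradicts itself.

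A fourth is that LLOQ/2 is one convention among several and has its own bias. This also stands, as the figures above show. The count and percentage of BLQ results need no distributional assumption and are the firmest part of the request.

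A reader might go further and infer that accumulation will be overstated. The documents do not support that: no accumulation analysis is planned, and the Cycle 2 and Cycle 4 troughs may be biased alike. Nor can one say that the SD is understated as a rule.

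**Conclusion.** The concern holds in conditional form. Where BLQ results occur, the SAP 9 rule gives location estimates that are too high and a CV that is too low, and nothing else in the plan corrects or discloses this. The direction is certain. The size is not known from the documents and rests on an assumed log-normal shape, BLQ share and CV. Over CV 50% to 100%, inflation of the arithmetic mean runs from 7–9% at 10% BLQ to 36–60% at 50%, and of the geometric mean from 10–18% to 46–94%. Predose Cycles 2 and 4 and the 30-Day Follow-up are the visits most exposed.

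Severity is minor. PK appears in none of the unredacted objectives or endpoints, the analysis is descriptive, and ORR, DOR and safety results are unaffected. It would be wrong to infer that the trial's conclusions are at risk.

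**What to change.** Replace the exclusion sentence in SAP 9 with a rule that:

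- counts a BLQ result as non-missing for the PK analysis population in SAP 3.12.5;
- reports n and % BLQ for each analyte and visit;
- keeps BLQ samples in the summaries at a stated value, such as LLOQ/2;
- reports the median as BLQ when it falls below the limit, and likewise the minimum and quartiles (order statistics above the limit do not depend on the substituted value);
- flags means and geometric means as unreliable when the BLQ share is high, with the threshold fixed in advance.

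The cost is a few lines of SAP text and a column or two in the concentration table. Means at affected visits will be lower than under the present rule. The price is that LLOQ/2 understates the mean, by 14.5% in the worst case computed (CV 30%, 50% BLQ), and inflates the CV when true variability is low. Its error in the mean and geometric mean was smaller than that of exclusion in every case computed for CV 30% to 100%.
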